## 7.0 EXPECTED RISKS AND UNANTICIPATED PROBLEMS

# 7.1 Expected Risks:

#### 7.1.1 HIIT:

The risks of short-term HIIT treatment are minimal for these patients. Mild muscle soreness associated with beginning any new exercise program is possible. The exercise program will be individualized for each patient, reducing the chances of soreness. With any exercise, there is a small risk for syncope, as well a cardiovascular event. Because of the short nature of the high intensity bouts, risk of syncope is reduced; rest periods also allow for greater blood flow, reducing risk of syncope. Patients at risk for any such cardiovascular event will be excluded. These types of adverse events as a result of HIIT, are extremely rare.

## 7.1.2 Blood Draws & Urine Collection:

Patients will need to undergo blood draws at the beginning and end of HIIT treatment. The second blood draw will be done under general anesthesia at the time of surgical staging. Risks to blood draws are minimal and include pain and discomfort, infection and hematoma. Thus, these women have little increased risk secondary to blood draws. Blood will be obtained by phlebotomists or by anesthesiologists/nurse anesthetists in the operating room. Patients will need to undergo urine collection at the beginning and end of HIIT treatment. Risks to urine collection are minimal.

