We predict that the HIIT intervention will result in decreased proliferation and increased apoptosis when comparing tumors pre- and post-HIIT. Based on our experience with this HIIT protocol in various special populations, EC patients are anticipated to demonstrate good compliance and report sufficient tolerability to the intervention. In addition, we anticipate that hyperactivation of the insulin/IGF-1/AMPK/mTOR pathway and stimulation of fatty acid/lipid biosynthetic pathways will be found in the endometrial tumors pre-HIIT, and HIIT therapy will result in inhibition of downstream targets of these metabolic pathways. Moreover, we expect BMI, waist-to-hip ratio, and HgBA1C to decrease. Elevated pre-treatment serum levels of fatty acids and glycolipids should be found in those obese/overweightwomen who best respond to HIIT, indicative of a more insulin-resistant metabolic phenotype in HIIT-responders. This insulin resistant metabolic profile should improve with HIIT treatment.

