Potential prospective subjects will be seen in private clinic rooms by the physician and the team member that will be informing and consenting the subject. The purpose of this study and the risks and side effects of HIIT therapy will be addressed in the consent and verbally explained to the patients. The purpose of serum and tissue collection and the risk to these procedures will be verbally explained to the patients. Informed consent will be obtained from the patients by the study coordinator.

In order to ensure retention of subjects during the proposed HIIT intervention, subjects will be contacted weekly by study staff. These scheduled calls or text messages will ensure that the subjects have no questions about the intervention, that they are tolerating HIIT without any significant adverse effects, that they are syncing their Fitbits, and to make sure they are logging in their exercises on the website every time they work out. Furthermore, subjects will be provided multiple contact numbers for study personnel to contact with questions or concerns about the HIIT intervention (day or night).

After women have undergone hysterectomy/surgical staging for EC or CAH, their corresponding pre-treatment endometrial biopsies and post-treatment endometrial tissue/hysterectomy specimens will be obtained for comparison. Hysterectomy/tumor and repeat endometrial biopsy specimens from the EC and CAH patients in the operating room will be collected via the Tissue Procurement Core Facility (TPF) at the Lineberger Comprehensive Cancer Center (LCCC). In addition, the pre-operative endometrial biopsy slides and blocks will be obtained from referring physicians of these patients for analysis in this study. All patients would have had an endometrial biopsy performed prior to referral to the Gynecologic Oncology clinic as part of their diagnosis of endometrial cancer or complex atypical hyperplasia. Blood (10mL) and urine will be collected pre- and post-HIIT intervention for metabolomic profiling as a strategy to identify other potential biomarkers of response to HIIT. Fresh EC tissue will be collected post-HIIT intervention via hysterectomy for metabolomic profiling and correlation with metabolic changes in serum. These biospecimens will be stored indefinitely for research purposes unless the participant refuses to agree to storage for future use on the informed consent form.

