- 5.3.5 To assess improvement in cardiorespiratory fitness with the HIIT intervention, peak oxygen consumption (VO2peak) will be measured preand post-HIIT. VO2peak is the gold standard for identifying fitness level and evaluating cardiovascular effects. This test will be used to establish individual training intensity. All participants will perform a ramp based cycling ergometer test with respiratory gases continuously monitored with open-circuit spirometry using a calibrated metabolic cart (True One 2400®, Parvo-Medics, Inc., Provo, UT). Data will be averaged over 15-second intervals, with the highest 15-sec oxygen consumption, minute ventilation, and heart

rate recorded as the peak oxygen consumption (VO2peak), time to exhaustion, and maximum heart rate, respectively.

- **5.3.6** To correlate improvement in obesity/overweight and insulin resistance with response to HIIT treatment, BMI, waist-to-hip ratio, body composition, HgBA1C, and diabetes status will be documented pre- and post-intervention. HgBA1C will be obtained pre-intervention only for all subjects. Body composition and visceral fat will be determined using portable ultrasonography as previously validated by our group. The Homeostasis Model Assessment Score [fasting insulin (microunits/ml) X fasting glucose (mmol/22.5)], a measurement of insulin resistance, will be calculated prior to and after the intervention.
- **5.3.7 To test if the metabolic profiles of blood and tumor correspond to HIIT responsiveness,** untargeted metabolomic/lipidomic analysis will be performed on (1) blood pre- and post- HIIT and (2) tumor pre- and post-HIIT intervention. Metabolic profiles of blood and tumor will be compared between pre- and post-intervention and the HIIT group. Untargeted metabolomic and lipidomic profiling will be performed using Ultrahigh Performance Liquid Chromatography-Tandem Mass Spectroscopy (UPLC-MS-MS) and Differential Mobility Spectroscopy-MS-MS (DMS-MS-MS). Urine is also being banked pre- and post-HIIT intervention for potential future metabolomic/lipidomic analysis.
- **5.3.8** Removal of Patients from Protocol Patients will be removed from the study if they indicate that they no longer wish to participate. Patients will be removed from study when any of the exclusion criteria listed in eligibility criteria apply.

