# CONFIDENTIAL UNIVERSITY OF NORTH CAROLINA

# 6.0 TIME AND EVENTS TABLE

# 6.1 Time and Events Table

	Pre-op or New visit	Baseline Testing Visit 	At home intervention 	Surgery	Post Surgical Testing Visit
	SOC appointment	During SOC appointment or at Applied Physiology Lab	4 to 8 Sessions	As scheduled per SOC	SOC appointment 2 to 4 wks post-surgery
Consent	X				
Eligibility Assessment	X				
Archival Tissue Retrieval	X				
Urine Sample	X			X	
Blood Sample	X			X	
Enrollment		X			
Waist and Hip Measurements		X			X
VO2peak		X			X3
Body Mass ultrasound		X			X
Visceral fat ultrasound		X			X
Fitbit Fitting		X			
Introduction to Fitness Plan		X			
Exercise Enjoyment Scale		X			X
Completion of Fitness plan			X		
Sync Fitbit data			X		
Participant Website Login			X		
Endometrial biopsy				X	
Hysterectomy Specimen				X	
Closing interview					X

Baseline visit can occur during SOC visit at time of consent and enrollment, or the subject will have the option to return to campus and perform visit at the exercise physiology lab at Fetzer Hall. If subject commits to return for baseline visit, but fails to return, the subject will not be enrolled on the study, and a new subject can be enrolled in that spot.

At home intervention begins with first HIIT session. During this time, subject will be called or texted by the study team to remind the subject to login to website, sync data, and troubleshoot technical difficulties.

The VO2 peak testing is optional at this visit.

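### Post-HIIT blood is drawn under general anesthesia and baseline blood at a clinic visit, so the mean pre-post metabolomic change within the HIIT arm cannot be attributed to HIIT alone

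*Combined protocol and SAP*

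**What the plan says.** The Time and Events Table (Section 6.1) marks the blood sample in two columns only: the first visit ("Pre-op or New visit"), which is also where consent and eligibility are handled, and surgery. Section 7.1.2 gives the condition of the later draw: "The second blood draw will be done under general anesthesia at the time of surgical staging". It adds who draws: "Blood will be obtained by phlebotomists or by anesthesiologists/nurse anesthetists in the operating room".

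Section 5.3 gives the purpose: "Blood (10mL) and urine will be collected pre- and post-HIIT intervention for metabolomic profiling". Section 5.3.7 gives the analysis: "untargeted metabolomic/lipidomic analysis will be performed on (1) blood pre- and post- HIIT". Section 5.1 gives the expected reading: "This insulin resistant metabolic profile should improve with HIIT treatment".

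No section sets or records prandial state, time of day or position relative to induction for either sample. In the current protocol text, fasting is mentioned only inside the HOMA formula of Section 5.3.6, not as a collection rule for these samples.

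The updated analysis plan (Section 8.2, Data Analysis Plans) tests the within-arm change against zero for Ki-67 and VO2peak. It adds an exploratory ANCOVA of HIIT versus the 10 usual-care completers and says that other variables may be treated similarly. It does not name metabolomics.

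**The concern.** A paired comparison isolates the intervention only if nothing else changes systematically between the two measurements. Here one thing changes for every patient by design: the first sample comes from a clinic patient and the second from a patient under general anesthesia. A difference shared by all patients does not shrink as patients are added, and no choice of paired test removes it.

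At stake is the claim that HIIT improves the circulating metabolic profile, which is part of the study's mechanistic argument. The protocol already applies the same reasoning to tissue: Section 5.3 adds a repeat endometrial biopsy at surgery so that a difference in specimen type is not mistaken for an effect of HIIT. Blood has no equivalent safeguard.

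**Working it through.** The plan gives no effect size, SD, alpha or power for metabolomics, so there is no figure to reproduce. The check is mainly structural.

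**1. What the change estimates.** For one metabolite, assume additive effects: θ is the HIIT effect, δ the effect of sampling conditions, and τ any other change over time.

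- Mean change in the HIIT arm: θ + δ + τ
- Mean change in usual care, if sampled under the same two conditions: δ + τ
- Difference between arms: θ

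If the plan is followed, sampling condition and time are the same variable within the HIIT arm, so θ and δ cannot be separated there. They can be separated in the between-arm difference, provided δ is common to both arms.

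**2. Which analyses are exposed.**

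| Analysis | Uses the anesthetized blood? | Affected by δ? |
|---|---|---|
| Ki-67 (tissue) | No | No |
| VO2peak | No | No |
| Pre-treatment blood in responders versus others (Section 5.1) | No | Not by anesthesia; prandial state still uncontrolled |
| Correlation of tumor profile with serum change (Section 5.3) | Yes | Not by a shift equal in all patients; possibly by one that varies |
| Mean pre-post change in blood profile (Sections 5.3.7 and 5.1) | Yes | Yes, fully |

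**3. Illustration under assumed shifts.** Inputs: n = 20 (Section 8.1); θ = 0; assumed two-sided alpha of 0.05; assumed shift k in SDs of the paired change. For a one-sample t-test the noncentrality is k√20, with 19 df and critical value 2.093. The last column is a simulated signed-rank test (20,000 runs, normal changes).

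| k | k√20 | Rejection rate, t | Rejection rate, signed-rank |
|---|---|---|---|
| 0 | 0 | 5.0% | 4.6% |
| 0.25 | 1.118 | 18.6% | 18.1% |
| 0.50 | 2.236 | 56.5% | 53.6% |
| 0.75 | 3.354 | 88.9% | 87.4% |

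These rates would follow from any common bias of that size. They show sensitivity at n = 20 and do not measure this trial's shift.

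**4. Precision of the contrast with usual care.** In SDs of the change, the standard error of the within-arm mean is 1/√20 = 0.224. For 20 versus 10 it is √(1/20 + 1/10) = √0.15 = 0.387. With 28 df and two-sided 0.05, a t-test has power of:

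- 24% for a 0.5 SD difference (0.5/0.387 = 1.29)
- 46% for 0.75 SD (0.75/0.387 = 1.94)
- 70% for 1.0 SD (1.0/0.387 = 2.58)
- 85% for 1.2 SD (1.2/0.387 = 3.10)

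**5. Effect of moving the draw part-way.** If usual-care post-samples were all anesthetized, only HIIT patients also sampled under anesthesia compare with them like for like. A sampling-condition covariate does not avoid this: that condition would vary only within the HIIT arm, so the adjusted arm difference still rests on the anesthetized HIIT patients. With m such patients the standard error is about √(1/m + 1/10). For an assumed m = 10 it is √0.2 = 0.447, against 0.387 for m = 20.

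**The case against.** Several points on the other side stand.

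- A reader might infer that prandial state differs in every patient. The documents do not state it at either draw, so it is an uncontrolled factor that may differ, not a documented difference.
- A reader might take the rejection rates as the size of the problem. The documents support neither the assumed shift nor a per-metabolite test at 0.05; the signed-rank tests in Section 8.2 are planned only for Ki-67 and VO2peak.
- A reader might extend the point to all the metabolomic work. Section 5.1 also looks for pre-treatment profiles that mark responders, and those analyses do not use the anesthetized sample.
- A reader might apply it to HOMA. "Homeostasis Model Assessment Score [fasting insulin (microunits/ml) X fasting glucose (mmol/22.5" implies fasting samples that the schedule does not show, but nothing says HOMA comes from these two draws. That inconsistency in Section 5.3.6 is a separate matter.
- A usual-care comparison is already allowed for other variables in Section 8.2. What is missing is a commitment for metabolomics, and evidence that usual-care blood was drawn under the same conditions, which the current text does not describe.
- A required fasted baseline would be awkward, because that draw is scheduled at the consent visit.

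These points narrow the concern. They do not answer the anesthesia contrast, which is explicit in the protocol and coincides with time in the HIIT arm. The comparison sentence in Section 5.3.7 is unclear about which groups are compared, so it cannot be read as a commitment to a control contrast.

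**Conclusion.** The point holds for one quantity: the mean pre-post change in the blood metabolomic and lipidomic profile within the HIIT arm. As planned, it cannot be attributed to HIIT, because an effect of anesthesia on the profile would be indistinguishable from it. The size and direction of that effect cannot be derived from the documents, and it could hide a HIIT effect as well as mimic one.

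This conclusion rests on the schedule and Section 7.1.2 being followed as written. It does not reach the Ki-67 primary endpoint, VO2peak or the analyses of pre-treatment blood. The exploratory objectives are not shown in the available text of Section 2.2, so the full metabolomic aim could not be read. The change is worth making because it is cheap and removes a built-in bias, not because the trial's main result is threatened.

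**What to change.** (a) For remaining patients, take the existing post-HIIT research sample before any anesthetic drug is given, for example when the intravenous line is placed. Record hours since food and draw time relative to induction for both samples. Do not require a fasted baseline.

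(b) In Section 8.2, name metabolomics in the exploratory HIIT versus usual-care ANCOVA, and make that contrast the basis for attributing metabolomic change to HIIT. First confirm that usual-care blood was drawn under the same two conditions. Then compare anesthetized post-samples with anesthetized post-samples, or include a sampling-condition covariate. Report the within-HIIT change as descriptive, with the sampling limitation stated, and align Sections 5.3.7 and 5.1 with this.

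Cost: no added draw or visit, two recorded items per sample, and some analysis wording. The downsides are real. Sampling conditions will differ between earlier and later patients, and HIIT patients sampled before anesthesia add little to the like-for-like contrast if all controls were sampled under it. With 10 controls that contrast is imprecise and should be presented as hypothesis-generating. If the draw cannot be moved, part (b) and the stated limitation still apply.

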## 7.1.3 Endometrial biopsy:

Endometrial Biopsy is a common gynecologic procedure performed in the outpatient setting. The risks of repeat endometrial biopsy at the time of surgery are minimal for these patients, given that they will be under general anesthesia and are to undergo immediate hysterectomy. Endometrial biopsy will be performed using a standard pipelle device, routinely used in our outpatient clinic. The most common risks to the patient for this procedure are cramping and a vaso-vagal response. Other much rarer risks include uterine bleeding (usually due to previously undiagnosed coagulopathies), uterine perforation (0.1 - 1.3%), pelvic infection and bacteremia (<1%). These patients will already be familiar with the procedure of endometrial

# 7.1.4 Breach of Confidentiality:

Research data will be stored in a secure, password-protected server accessible solely to trained study staff. All data and specimens stored in the research database will be given a unique research ID that will be blinded to investigators with the exception of the Study Coordinator, who will function as an honest broker. The Study Coordinator will be trained and certified in research ethics and HIPAA tenets.

## 7.2 Definition

As defined by UNC's IRB, unanticipated problems involving risks to study subjects or others (UPIRSO) refers to any incident, experience, or outcome that:

- Is unexpected (in terms of nature, severity, or frequency) given (a) the
  research procedures that are described in the protocol-related documents,
  such as the IRB-approved research protocol and informed consent
  document; and (b) the characteristics of the subject population being
  studied;
- Is related or possibly related to a subject's participation in the research; and
- Suggests that the research places subjects or others at a greater risk of harm (including physical, psychological, economic, or social harm) related to the research than was previously known or recognized.

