#### **5.3.1 Structured Interview:**

A structured one-on-one interview will occur with participants after completion of the HIIT program. The interview will be used to learn about barriers and concerns they experienced with regard to the current training protocol; preference of exercise mode and instruction; and opinions on what information participants would find helpful to improve the at-home training experience. While we do not intend to formally analyze the interview responses, we do anticipate that they will be useful for refining our intervention program for future trials.

- **5.3.2 Tolerability, Feasibility, Compliance, and Adherence:** Adherence and tolerability will be evaluated based on number of sessions attended/completed, modifications, such as change in mode, number of training days per week, and recovery days needed between sessions to complete training. The physical activity enjoyment scale will be given to assess participant enjoyment of exercise during the baseline and post-surgical testing visit.
- 5.3.3 To determine if HIIT decreases proliferation and induces apoptosis in the endometrial tumors, tissue microarrays (TMAs) will be constructed and immunohistochemical (IHC)analysis performed to assess Ki-67 staining (marker of proliferation) and caspase-3 expression (marker of apoptosis). The percentage of Ki-67 positive cells, termed the Ki-67 index, will be calculated pre- and post-treatment. Apoptosis will be evaluated by changes in activated caspase-3 expression. Individual slides will be digitized and analyzed using the Aperio ScanScope (Aperio Technologies, Vista, CA). This work will be performed with the expertise of the UNC-CH Translational Pathology Lab (TPL).
- **5.3.4** To test if HIIT alterations inhibits downstream targets of the insulin/IGF-1/AMPK/mTOR signaling pathway, IHC analyses of the ECs will be performed to determine expression of key targets of the insulin/IGF-1/mTOR pathway pre- and post-intervention, including p-IRS-1, p-IGF1R, p-AMPK, p-mTOR, p-Akt, p-S6, and p-4EBP-1.

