# 7.3 Reporting

Any UPIRSO that occurs during the conduct of this study and that meets all three criteria listed in 9.4.3 must be reported to the UNC IRB using the IRB's web-based reporting system.

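### Tolerability of home HIIT is scored from session counts alone, and nothing visible in the plan requires exercise-related adverse events to be recorded or summarised

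*Combined protocol and SAP*

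**What the plan says.** **Outcome.** Section 5.3 lists tolerability, with efficacy, adherence and enjoyment, among the secondary outcomes. Section 5.3.2 defines it: "Adherence and tolerability will be evaluated based on number of sessions attended/completed, modifications, such as change in mode", followed by training days per week and recovery days between sessions. An enjoyment scale is given at baseline and after surgery.

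**Data and analysis.** Table 6.1 has rows for items as small as Fitbit fitting and website login, but none for adverse events. The analysis plan in 8.2 names Ki-67, VO2peak, p-mTOR and time to exhaustion as examples and mentions no safety variable. The closing interview (5.3.1) will not be formally analysed.

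**Safety text.** Under 5.3, staff contact patients weekly, partly to check "that they are tolerating HIIT without any significant adverse effects". Section 7.4 provides continuous safety monitoring by the principal investigator, periodic reports to the DSMC, and minuted team meetings that cover safety.

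**Reporting to the IRB.** Section 7.1.1, under expected risks, states "With any exercise, there is a small risk for syncope, as well a cardiovascular event" and calls such events extremely rare. Section 7.2 defines an unanticipated problem by three criteria: "Is unexpected (in terms of nature, severity, or frequency"; "Is related or possibly related to a subject's participation in the research; and"; and "Suggests that the research places subjects or others at a greater risk of harm" than was known before. Section 7.3 requires a report of any such problem "that occurs during the conduct of this study and that meets all three criteria listed in" section 9.4.3.

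**The concern.** A tolerability outcome for a new exercise programme would normally include what happened to patients while they exercised. Here the definition measures how much exercise was done. The two can diverge: an event may leave the session count unchanged, and a low count may have nothing to do with toxicity.

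Three statements in the protocol raise the stakes. It presents this as the first trial of HIIT in endometrial cancer patients. It says these patients are most likely to die of cardiovascular disease. It also supports HIIT partly by citing few or no adverse events in other populations (1.1, 1.2). A trial that does not collect such events cannot add to that evidence, and could report good tolerability without its toxicity data. Events not recorded at the time cannot be reliably recovered at analysis.

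**Working it through.** The plan states no adverse-event rate or safety figure, so there is nothing to reproduce. The check traces an exercise-related event through the plan.

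**1. What the 5.3.2 rule returns.**
- A patient faints after a session and still completes her programme without modification: full session count, scored as tolerating.
- A patient stops short of four sessions because of symptoms, and another because surgery is brought forward: if their counts match, the measures listed do not separate them. The rule shows that the programme was cut short, but not why.

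**2. Whether another part of the plan captures the event.**

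| Place | What it offers | What is missing |
|---|---|---|
| 5.3, weekly contact | A question about significant adverse effects | Any rule to record the answer |
| 5.3.1, closing interview | Barriers and concerns | Formal analysis |
| Table 6.1 | 19 rows of scheduled items | An adverse-event row |
| 7.4 | Investigator monitoring, DSMC reports, minutes | Defined content of the reports |
| 7.2 and 7.3 | Reports to the IRB | Any bearing on the trial dataset |
| 9.4.3, violations | Report within one week if a participant was harmed | Cover for events with no protocol variance |
| 8.2 | Descriptive statistics for relevant variables | Any named safety variable |

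So an event may well be noticed, but no visible step turns it into data. Nor does the visible text give an adverse-event definition, grading scale, collection window or attribution rule.

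**3. Which patients would be counted.** Section 8.1 continues accrual until 20 patients have complete pre- and post-HIIT data. A patient who stops because of an event and has no post-HIIT data is not among the 20. Section 8.2 allows attrition up to 10%: 20 / (1 - 0.10) = 22.2, so about 22 or 23 patients would start and two or three would fall outside the evaluable set. The documents do not say why patients would leave, but any who leave because of toxicity would be in this group.

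**4. The cross-references.** Section 7.3 sends the reader to 9.4.3 for the three criteria. They stand in 7.2, and the closing paragraph of 9.4.3 points back to 7.2.

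**The case against.** The strongest reply is that the plan does watch for harm. Staff ask about adverse effects weekly, patients have contact numbers day and night, the investigator monitors safety continuously, and the DSMC receives reports that are not limited to unexpected events. Case report forms are not shown, table 6.1 is not declared a complete list of data collected, and the variable list in 8.2 is open-ended. The text of section 2.2 did not survive extraction, so it may contain a safety objective. Tolerability is called a secondary outcome in one sentence of 5.3, while section 3 visibly lists only the Ki-67 endpoint.

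Most of this stands, and it limits the point to recording and summary. It does not remove it, because 5.3.2 gives an explicit rule for tolerability and that rule contains no events.

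Three stronger readings are tempting, and the documents do not support them:

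- *A reader might infer that unanticipated-problem reporting is the only reporting rule.* It is not. Section 7.4 provides DSMC reporting, and 9.4.3 covers harmful protocol violations without any test of unexpectedness.
- *A reader might infer that risks listed in 7.1.1 are exempt from reporting.* The first criterion covers severity and frequency as well as nature. Against risks described as extremely rare, a severe or repeated event could still qualify if the other two criteria are met.
- *A reader might size the gap by the one-sided 95% upper bound for no events in 20 patients, 1 - 0.05^(1/20) = 13.9%.* That bound is a property of the sample size. It would be the same under a complete adverse-event plan, and 20 is the evaluable number rather than the number who start HIIT.

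The misdirected reference in 7.3 is editorial, since a reader still reaches the criteria.

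**Conclusion.** The point holds as a gap in outcome definition and data capture. Tolerability is measured by exercise completed, and no visible text requires exercise-related events to be recorded or summarised. The trial could therefore report good tolerability without toxicity data. It does not follow that events would go unnoticed or be withheld from the DSMC; the documents leave both open.

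The gap has no numerical size. It affects one named secondary outcome, for all patients who start HIIT, and leaves the Ki-67 analysis untouched. The conclusion assumes that neither section 2.2 nor the unseen case report forms contain an adverse-event item. If they do, what remains is to bring 5.3.2, table 6.1 and 8.2 into line with them.

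**What to change.** 1. Add an adverse-event row to table 6.1 covering the at-home period and the post-surgical visit.
2. At the weekly contacts and the post-surgical visit, record any event during or after a HIIT session, with its date, seriousness, relation to HIIT and whether sessions were stopped or modified.
3. Add these events to the definition of tolerability in 5.3.2.
4. Summarise them in 8.2 for all patients who start HIIT, not only the 20 evaluable, and include them in the results and the DSMC report whether or not they were expected.
5. Reconcile 7.1.1 with 7.2 and 7.3, so that it is clear how an event listed as an expected risk is handled, and correct the reference to 9.4.3.

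The cost is protocol wording and one case report form page. With about 2-3 weeks of HIIT, weekly contact means two or three entries per patient, plus one at the post-surgical visit. No visit or procedure is added, and the exercise prescription is unchanged. The report should say which patients were treated before the form existed, because their events were not collected under this rule.
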